3.2 Sample Size

A total of 2700 deaths **were planned to** be observed in order to exclude a hazard ratio (darbepoetin alfa to placebo) of 1.15 with a 1-sided significance level of 0.025. With 2700 deaths, the study is powered at just over 90% if the true hazard ratio is 1.0 (approximately 93%). To observe 2700 deaths, the study **planned to** randomize a total of 3000 subjects which assumes a 7-year enrollment period, a 3-year follow-up after last subject enrolled, a 1-year survival rate of 51% (Sandler et al, 2006), and a common exponential drop-out rate of 0.0511.

Excluding a hazard ratio of 1.15 corresponds to excluding a decrease in median survival of approximately 1.6 months in the darbepoetin alfa arm group compared to placebo. The estimated decrease in survival has equipoise with the decreased risk of the need for RBC transfusions. This estimation assumes survival time is exponentially distributed which allows for a conversion from a hazard ratio to medians (i.e., hazard ratio = median_{placebo}/median_{darbepoetin alfa}). A median survival of 12.3 months (Sandler et al, 2006) was assumed in the placebo arm in order to derive the difference in medians that corresponds to a hazard ratio of 1.15.

The study was terminated early based on a recommendation by the independent Data Monitoring Committee with a sample size of 2549 subjects. The study was closed to further

enrollment as of 8 May 2017 and the last data are anticipated to be collected as of 7 June 2017.

4. Covariates and Subgroups

4.1 Planned Covariates

- Stratification factors:
 - Geographic region (some regions may be combined for analysis):
 - Region 1: Belgium, Germany, Israel, Italy, Luxembourg, Netherlands, Spain, Switzerland, South Africa, UK
 - Region 2: Bulgaria, Czech Republic, Greece, Poland, Romania, Russia, Serbia, Slovenia, Ukraine
 - Region 3: Argentina, Brazil, Chile, Hong Kong, South Korea, Malaysia, Mexico, Philippines, Taiwan
 - Region 4: India
 - Region 5: Canada, United States (reference group)
 - Region 6: China
 - Region 7: Japan (analyzed as part of Region 3)
 - Histology: Squamous vs non-squamous cell (reference group)
 - Screening hemoglobin level: <10 g/dL vs >=10 g/dL (reference group)
- Potentially clinically important covariates:
 - NSCLC platinum-based chemotherapy vs. other chemotherapy (reference group)
 - NSCLC Targeted therapy (anti-EGFr or anti-angiogenic agents or other) vs. none (reference group)
 - o Baseline serum erythropoietin: ≤100 mU/mL vs >100 mU/mL (reference group)
 - History of VTEs: yes vs. no (reference group)

Note that the reference group will be coded a "0" in any statistical modeling including stratification factors and/or covariates.

4.2 Subgroups

The subgroup of subjects who were not impacted by the early study closure to may be analyzed as a sensitivity analysis for the primary and secondary endpoints (overall survival, progression-free survival and incidence of transfusion or hemoglobin ≤ 8 g/dL) as well as the analyses of investigational product dosing and changes in dosing. For the analysis of overall survival, this would include subjects who were lost to follow-up or who died prior to 8 June 2017. For progression-free survival, this would include subjects who were withdrawn, lost to follow-up or who died or had radiographic progression prior to 8 June 2017. For incidence of transfusion or hemoglobin ≤ 8 g/dL, investigational product dosing and changes in dosing, this would include subjects who were withdrawn, lost to follow-up or completed chemotherapy prior to 8 June 2017.

These subgroups and planned covariates will be re-examined and appropriately recategorized before the analysis. If a subgroup only contains less than 10% of the total study population, it will be combined with another subgroup in the analysis.

5. Definitions

Best Overall Response

A subject's best overall response during the study will be categorized in the following order: complete response, partial response, stable disease, disease progression, not evaluable, missing due to clinical progression, and missing for reasons other than clinical progression.

Change in hemoglobin from baseline to EOETP

The change score is the difference between the baseline hemoglobin value and the EOETP value (i.e., EOETP value – baseline value). Post-baseline hemoglobin values within 28 days after a RBC transfusion will not be used in the calculation of change. The last available post-baseline hemoglobin, not occurring in the 28 days after a RBC transfusion, will be used to calculate change in the event that the EOETP value is missing or occurred in the 28 days after a RBC transfusion. Subjects without a post-baseline value that did not occur in the 28 days after a RBC transfusion and subjects missing a baseline hemoglobin will be excluded from the analysis. Only central laboratory values will be used. Because the EOETP will vary by subject, the change in hemoglobin from baseline will also be summarized at specific time points of week 13 and week 16.

Event of Interest	Search Strategy	Scope
Ischaemic Heart Disease, including	Ischaemic Heart Disease SMQ	Narrow
MI		
Mortality and/or Tumor	Malignancies SMQ	Narrow
Progression		
Cerebrovascular disorders	Central nervous system vascular	Narrow
	disorders SMQ	
Hypertension	Hypertension SMQ	Narrow
Cardiac failure	Cardiac failure SMQ	Narrow
Thromboembolic events, venous	Embolic and thrombotic events,	Narrow
	venous	
Convulsions	Convulsions SMQ	Narrow & Broad
Severe cutaneous reactions	Severe cutaneous reactions SMQ	Narrow & Broad
Hypersensitivity	Hypersensitivity SMQ	Narrow & Broad
PRCA	Antibody-mediated Pure Red Cell Aplasia AMQ	

Events of Interest (EOI): EOIs for Aranesp are as follows:

Hemoglobin Threshold

A hemoglobin that increases to >12 g/dL at any time during the treatment period is considered to have exceeded the threshold. This increase will be summarized both by including and excluding hemoglobin values that occurred in the 28-day period following an RBC transfusion.

Medications of Interest (MOI): MOIs for Aranesp Oncology are as follows based on values as of **Q2 2017** or later:

Antihypertensives
Antimicrobials
Antithrombotic agents
Colony stimulating factors
Epoetins
Histone deacylating inhibitors
Hypomethylating agents
Iron
Iron chelating agents
Lenalidomide
Methotrexates
Platelets
Platelets Thalidomide

Non-response (to investigational product)

A non-responder is a subject who, after study day 35, received two transfusions that are \geq 21 days apart and \leq 42 days apart.

Objective tumor response rate (ORR)

The incidence of a complete or partial response at any time during the study. Response will be determined by the investigator's assessment of the scans using the version of RECIST specified in the protocol at the time of subject enrollment.

Overall survival (OS)

Time from randomization to date of death. Subjects will be censored on the date of last contact (ie, the date the subject was last known to be alive) if they are not known to be dead.

Progression-free survival (PFS)

Time from randomization to date of radiographic disease progression or death from any cause, whichever event occurs first. Subjects without either event will be censored on the date of their last disease assessment. Disease progression will be based on the investigator's assessment of scans using the version of RECIST specified in the protocol at the time of subject enrollment.

Rate of rise in hemoglobin >1.5 g/dL in 21 days

The occurrence of a hemoglobin that increases by >1.5 g/dL in any 21-day period in the treatment

period. This will be summarized both by keeping a 21-day window after each RBC transfusion and **excluding** a 21-day window after each RBC transfusion.

RBC transfusion or hemoglobin ≤8.0 g/dL from week 5 (day 29) to EOETP

Any RBC transfusion (packed RBCs or whole blood) given or a hemoglobin ≤8.0 g/dL on or after study day 29 until the EOETP, inclusive.

RBC transfusion or hemoglobin ≤8.0 g/dL from week 1 (day 1) to EOETP

Any RBC transfusion (packed RBCs or whole blood) given or a hemoglobin ≤ 8.0 g/dL on or after study day 1 until the EOETP, inclusive.

RBC transfusion from week 5 (Day 29) to EOETP

Any RBC transfusion (packed RBCs or whole blood) given on or after study day 29 until the EOETP, inclusive.

RBC transfusion from week 1 (Day 1) to EOETP

Any RBC transfusion (packed RBCs or whole blood) given on or after study day 1 until the EOETP, inclusive.

Thrombovascular event (TVE)

Thrombovascular events are adverse events that include arterial thromboembolic events (ATEs), venous thromboembolic events (VTEs), and unspecified/mixed thromboembolic events. These events will be coded using MedDRA version **20.0** (or higher) and identified using a Standardized MedDRA Query (SMQ 2000081, "embolic and thrombotic events") or more appropriate query available at the time of analysis. **Arterial thromboembolic event (**ATEs**)**, **Venous thromboembolic event (**VTEs**) and Unspecified/mixed thromboembolic events** are described below:

• ATE

ATEs include stroke, transient ischemic attack (TIA), acute coronary syndromes (ACS), and other arterial thrombosis/embolism. These events will be coded using MedDRA version **20.0** (or higher) and identified using the sub-SMQ 20000082 ("embolic and thrombotic events, arterial") or more appropriate query available at the time of analysis.

• VTE

VTEs include deep vein thrombosis (DVT), pulmonary embolism (PE), and other venous thrombosis excluding superficial venous thrombosis. These events will be coded using MedDRA version **20.0** (or higher) and identified using the sub-SMQ 20000084 ("embolic and thrombotic events, venus") or more appropriate query available at the time of analysis. In

addition, VTEs will be distinguished by whether or not they were confirmed by imaging. The primary analysis of VTEs will include fatal VTEs and VTEs confirmed by imaging; a sensitivity analysis will summarize all VTEs regardless of severity or confirmation.

Unspecified/mixed thromboembolic event

Unspecified/mixed thromboembolic events include thromboembolic events where the vessel type is either unspecified or a mix of arterial and venous. These events will be coded using MedDRA version **20.0** (or higher) and identified using the sub-SMQ 20000083 ("embolic and thrombotic events, vessel type unspecified and mixed arterial and venous") or more appropriate query available at the time of analysis.

Time to Progression (TTP)

Time from randomization to date of radiographic disease progression. Subjects without progression will be censored on the date of their last disease assessment. Disease progression will be based on the investigator's assessment of scans using the version of RECIST specified in the protocol at the time of subject enrollment.

Treatment Group

Subjects were randomized to 1 of 2 treatment groups: darbepoetin alfa (500 μ g) Q3W or placebo Q3W in a 2:1 allocation.

Treatment-emergent Adverse Event

A treatment-emergent adverse event is an adverse reported via the adverse event summary eCRF with an onset date between study day 1 and 30 days after the last dose of IP, inclusive, with one exception: VTEs and adverse events associated with RBC transfusions can have an onset date of 30 days after the last dose of IP or the EOTP visit, whichever is later.

6. Analysis Sets

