9.2 Subject Accountability

The number and percentage of subjects screened, randomized, and who received at least one dose of investigational product will be presented (a footnote will include the date of first subject randomized and the end of study date). The number and percentage of subjects who withdrew prematurely will be tabulated by the reason for withdrawal. **Since the study was terminated early,**

the number of subjects who were still on-study as of the termination date (dosing terminated 8 May 2017; data collection terminated 7 June 2017) will be tabulated by treatment group.

The number and percentage of subjects in the primary analysis set, the radiographic endpoint primary analysis set, the transfusion from week 5 to EOETP primary analysis set, full analysis set, **and the safety analysis set** will be presented. The number and percentage excluded from the analysis sets will be tabulated by the reason for exclusion.

A cumulative distribution plot will depict subject randomization over time; this will include a footnote of the number of subjects randomized but not dosed. In addition, the number and percentage of subjects randomized will be tabulated by study site and by the stratification factors (ie, geographic region, tumor histology and screening hemoglobin value).

A cumulative distribution plot will depict subject discontinuation from the treatment period over time. Each reason for ending the treatment period will be depicted by a line with separate plots for each treatment group

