9.6 Safety Analyses

The following table summarizes the safety endpoints in this study, including the primary endpoint, overall survival, and the key secondary endpoint, progression-free survival.

Endpoint	Primary Summary and Analysis Method (Specify Analysis Set if FAS is Not Used)	Sensitivity Analysis	
Primary Safety Endpoint (primary endpoint of the study		()	
Overall Survival	Summarize the number of subjects with events and numbers of subjects censored, Kaplan-Meier quartiles, KM estimates of 1-year, 2-year, and 3-year	 Overall survival using: Full Analysis Set Overall survival using: Per- protocol Analysis Set 	

Table 9-1. Safety Endpoint Summary Table

	survival by treatment group. Present the hazard ratio with 95% confidence interval Dataset: Primary Analysis Set	•	KM time-to-event plots using the Primary Analysis Set, Full Analysis Set and Per-protocol Analysis Set Repeat analysis by stratification factors Dataset: Primary Analysis Set Repeat analysis for subjects impacted vs not impacted by early study termination Dataset: Primary Analysis Set Repeat analysis based on study day 1 rather than date of randomization Dataset: Full analysis set using targeted day 1 as the baseline use central laboratory hemoglobin values
Overall Survival	Cox proportional hazards regression modelling with treatment group in the model, stratified by the stratification factors. This will include the p-value testing for an interaction between treatment group and each stratification factor Dataset: Primary Analysis Set	•	Cox proportional hazards regression modelling including treatment group only. Dataset: Primary Analysis Set Cox proportional hazards regression modelling including the stratification factors and other clinically important covariates Dataset: Primary Analysis Set Results for stratification factors and covariates may be provided as a forest plot. Dataset: Primary Analysis Set
Overall Survival	Overall Survival with Adjustment for Cross-in using a Cox regression that estimates the hazard ratio with treatment group treated as a time- dependent covariate to account for cross-in of erythropoietic agent use by placebo Dataset: Primary Analysis Set		
Secondary	Safety Endpoint		

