- To explore the impact of cross-in (placebo subjects who begin erythropoiesis stimulating agents at any point after randomization), an analysis will be performed that models erythropoiesis stimulating agent use as a time-dependent covariate in the stratified Cox regression. For subjects randomized to the darbepoetin alfa arm, the time-dependent covariate will be coded "1" throughout the time course (with the exception of subjects randomized to darbepoetin alfa who mistakenly receive placebo; they will be coded "0" throughout the time course unless they begin use of any erythropoiesis stimulating agent). For subjects randomized to the placebo arm, the time-dependent covariate will initially be coded "0" and change to "1" if and when they begin use of any erythropoiesis stimulating agent. Because the time-dependent covariate is based on information post-randomization, the results of this analysis will be interpreted with caution.
- To assess the impact of misspecifications of the stratification factors at randomization, a hazard ratio with 95% confidence interval will be estimated from an unstratified Cox regression with treatment group as a covariate along with covariates that represent the stratification factors. The values of the stratification factors will be determined from the case report forms rather than the IVRS. This analysis will only be done if there is evidence that there were errors in the IVRS stratification factors.
- To assess the impact of the early termination of the study, the primary analysis will be repeated for subjects who were still on-study or in long-term follow-up

as of June 7 and for subjects who were not impacted by the early study termination.

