9.6.2 Secondary Safety Endpoint

The primary analysis of PFS will be based on the radiographic endpoint primary analysis set and will use a Cox regression model, stratified by the randomization factors, with treatment group as the only covariate. PFS will be measured from randomization to disease progression (as defined by the version of RECIST specified in the protocol at the time of subject enrollment) or death from any cause; subjects without either event will be censored at the last disease assessment date. If non-inferiority has been declared for OS, non-inferiority will be declared for PFS if the upper confidence limit for the hazard ratio is less than 1.15 using a 1-sided significance level of 0.025.

Sensitivity analyses for PFS will be done similar to those for the primary endpoint, OS, as further exploratory analyses for the secondary endpoint: However, the sensitivity analyses will be largely limited to the Radiographic Endpoint Primary Analysis Set (ie, few sensitivity analyses using the Per Protocol Analysis Set or any other data set are planned). In addition, a sensitivity analysis may be performed that examines the treatment effect by subgroups formed on the basis of which version of RECIST was used to evaluate the subject. If this analysis is performed, however, the results will need to be interpreted cautiously since the version of RECIST will be confounded with time of enrollment (RECIST 1.0 subjects will be enrolled first, RECIST 1.1 subjects second) and it is anticipated that less than 10% of the subjects will be evaluated with RECIST 1.0.

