	Imaging studies will be performed every 9 weeks (± 7 days) or at any time symptoms suggestive of disease progression occur. Subjects who discontinue chemotherapy or IP should continue to be evaluated radiographically Q9W until disease progression.	Every 8-10 weeks until progression
EOTP	The EOTP visit is the next Q3W visit (± 6 days) after disease progression	n/d
Long-term follow-up (LTFU)	 LTFU begins after disease progression. Visits should occur at 3-month intervals (± 2 weeks). and	n/d
EOS	EOS is when a subject dies or is lost to follow- up or withdrawal or until 22 June 2017	n/d

n/d Not determinable – since many of these are event driven, the period for an individual subject cannot be determined apriori

Additional description of per protocol analysis

• Exclude subjects with EN 111 or EN 101 or OT 903

This excludes:

a) subjects that did not have NSCLC (OT 903)

b) subjects that did not have metastatic (Stage IV) or advanced stage IIIB with malignant pleural effusion NSCLC (prior to Amendment 3) (ie, subjects that had a lower grade tumor)

• Exclude subjects with EN 117A

This excludes subjects with disease progression prior to study day 1

• Exclude subjects with EN 202

This excludes subjects with a history of or current cancer diagnosis of a cancer type other than NSCLC

• Exclude subjects with EN 109 or EN 117 B

This excludes subject who did not have a baseline pre-chemo scan prior to randomization

- Exclude subjects with an ECOG performance status > 1 at screening (EN 113 or EN 103)
- Exclude subjects with EN 114 or EN 105

This should exclude subjects that had a life expectancy < 6 months based on the judgment of the investigator at screening

- Exclude subjects who received any erythropoiesis stimulating agents within the 28 days prior to screening (EN 223 or 218)
- Exclude subjects with EN 210 This should exclude subjects with a documented history of pure red cell aplasia
- Exclude subjects who are not dosed per protocol through week 7 (however, include subjects who received a planned dose adjustment per section 6.1.2 of the protocol)
- Exclude subjects who did not receive first line chemotherapy with an initial start date on or before Study day 1 and an end date after Study day 1

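### The check on early termination picks its overall survival subjects by whether they died, and its counterpart set has no deaths to analyse

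*SAP*

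**What the plan says.** Section 4.2 describes a sensitivity subgroup of subjects not affected by the early closure. For OS: "For the analysis of overall survival, this would include subjects who were lost to follow-up or who died prior to 8 June 2017". The definition for progression-free survival (PFS) reads: "this would include subjects who were withdrawn, lost to follow-up or who died or had radiographic progression prior to 8 June 2017". The section says these sets may be analysed and will be re-examined before analysis, and that any subgroup below 10% of the population will be merged with another.

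Section 9.6.1 is firmer. To judge the effect of early termination, "the primary analysis will be repeated for subjects who were still on-study or in long-term follow-up" as of 7 June, and also for subjects not affected. The OS row of the safety endpoint table in Section 9.6 lists the same item: "Repeat analysis for subjects impacted vs not impacted by early study termination". Section 9.6.2 carries it to PFS: "Sensitivity analyses for PFS will be done similar to those for the primary endpoint, OS".

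On dates, Section 9.2 has "data collection terminated 7 June 2017", and Section 7.2 counts only deaths on or before the termination date. The visit table in Appendix A ends a subject's study at death, loss to follow-up, "withdrawal or until 22 June 2017".

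**The concern.** The endpoint decides who is in the OS set. A subject randomized in 2016 enters it by dying and is excluded by surviving. That is right truncation on the event, and it shrinks any true treatment difference. The complementary set consists of people alive at the cut, so there is nothing to estimate an HR from.

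This is the SAP's only stated check on how early termination affected OS, in a trial whose primary endpoint is mortality and whose question is possible harm. A reader who sets this HR beside the primary one would take a selection artefact for an effect of stopping early. If the true HR is above 1, the artefact is falsely reassuring.

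**Working it through.** **Inputs.** From SAP Sections 3.1 and 3.2: 2549 subjects, 2:1 allocation, 1-year survival 51%, exponential drop-out 0.0511, margin 1.15, one-sided 0.025. From Sections 7.2 and 9.2: enrolment closed and dosing stopped 8 May 2017, data collection ended 7 June 2017. Actual accrual is not in the documents, so uniform accrual over 5 to 8 years is assumed. The planned rate of 3000 in 7 years would reach 2549 in 2549 × 7/3000 = 5.95 years.

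**Step 1: the plan's own figures.**
- Power = Φ(ln 1.15 × √(2700 × 2/3 × 1/3) − 1.96) = Φ(3.42 − 1.96) = 0.928, against a stated 93% or so.
- Deaths: λ = −ln 0.51 = 0.673, d = 0.0511 per year, θ = λ + d = 0.724. Then 3000 × (λ/θ) × [1 − (e^(−3θ) − e^(−10θ))/(7θ)] = 2726, against a stated 2700. A monthly drop-out rate would give 1566, so the unit is per year.

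**Step 2: why the OS set is biased.** Take a subject with u years left before the cut. Within the not-affected set, the death hazard is λ/(1 − e^(−θu)). The within-set HR is therefore

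HR × (1 − e^(−θu)) / (1 − e^(−θ′u)), with θ′ = HR × λ + d.

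For a true HR of 1.15, θ′ = 0.825:
- u = 5 years: 1.15 × 0.973/0.984 = 1.14
- u = 2 years: 1.15 × 0.765/0.808 = 1.09
- u = 1 year: 1.15 × 0.515/0.562 = 1.05
- u → 0: 1.15 × 0.724/0.825 = 1.01

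The nearer a subject is to the cut, the more of the treatment difference is removed. At a true HR of 1 the factor is 1.

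**Step 3: size over the whole trial.** Simulation used exponential survival and drop-out, a data cut 30 days after accrual ends, and an unstratified Cox model. With a true HR of 1.15 and 6000 replicates:

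| Accrual (years) | HR, all subjects | HR, not affected | Upper limit <1.15, all | Upper limit <1.15, not affected | Affected subjects | Their deaths by 7 June | Their deaths 8–22 June |
|---|---|---|---|---|---|---|---|
| 5 | 1.150 | 1.095 | 2.9% | 16.8% | 594 | 0 | 17.7 |
| 6 | 1.149 | 1.103 | 2.7% | 13.2% | 500 | 0 | 14.9 |
| 7 | 1.149 | 1.110 | 3.0% | 11.3% | 431 | 0 | 12.8 |
| 8 | 1.150 | 1.116 | 2.6% | 9.4% | 378 | 0 | 11.3 |

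For other true HRs (1000 replicates; accrual 5, 7 and 8 years), the not-affected set gives:
- true 0.85: 0.905, 0.892, 0.882
- true 1.00: 0.999, 1.001, 1.003
- true 1.30: 1.193, 1.226, 1.234

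The standard error at 7 years is about 0.048 in both analyses, because every death is kept. The confidence interval gives no sign of the problem.

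**Step 4: PFS.** Selection is of the same kind but weaker. With an assumed PFS median of 4 to 7 months and 15% of PFS events assumed to be deaths, a true 1.15 appears as 1.13–1.14. The chance of an upper limit below 1.15 is 4–6%, against 2–3%. The two definitions also overlap. A subject who progressed before 8 June is not affected under Section 4.2. If alive, that subject is usually in long-term follow-up, since "LTFU begins after disease progression" (Appendix A), and so is affected under the Section 9.6.1 wording. Under the same assumptions about 190–330 subjects fall in both sets.

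**The case against.** - **These are exploratory analyses.** Section 9.6.1 labels them so, and no non-inferiority decision attaches to either set. The 11% figure measures distortion; it is not a trial error rate. At true 1.15 the shift is ln(1.15/1.11) = 0.035, below one standard error of 0.048. All of this stands and limits the severity. But both analyses use the same deaths, so the gap between their HRs is mainly selection, and that gap is what the check asks readers to look at.
- **Section 4.2 is permissive.** It says the sets may be analysed and will be re-examined. Section 9.6.1 says the analysis will be repeated, and no corrected definition is given. The 10% rule would probably not trigger: the affected set is 378/2549 = 15% to 594/2549 = 23% at true 1.15. Merging would only recreate the full set.
- **Zero deaths depends on the cut.** This stands. Section 3.2 only anticipates 7 June, and Appendix A has 22 June. Under 22 June there would be about 11–18 deaths, too few to judge against 1.15.
- **The PFS overlap is inferred.** It arises only if Section 9.6.2 imports the Section 9.6.1 wording. Protocol Section 7.5 also sends some subjects without progression into long-term follow-up. The overlap is a point to clarify, and its count rests on assumed inputs.
- **A randomization-date set adds little.** Its HR should match the primary one, and with a 12-month limit some retained subjects are still censored by closure. That is fair, but the set is at least unbiased.

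**Conclusion.** The concern holds. Both OS faults follow from the SAP's definitions without simulation: membership of one set is decided by death, and the other has no deaths by 7 June 2017. At a true HR of 1.15 the not-affected set shows about 1.10–1.12 for 5 to 8 years of accrual, with a 9–17% chance of an upper limit below 1.15 against about 3% in all subjects. There is no bias at 1.00, and below 1 the estimate moves up toward 1.

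These sizes rest on exponential survival, uniform accrual and drop-outs counted as lost to follow-up. The OS definition, unlike the PFS one, does not mention withdrawn subjects, so they appear to belong to neither set. The primary OS analysis uses all dosed subjects with censoring at last contact and is not affected. The planned check on early termination should be corrected, but the fault does not threaten the main result.

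**What to change.** - For OS and PFS, replace the outcome-defined sets with all subjects randomized at least a pre-specified time before 8 May 2017 (12 months is one example), whatever their outcome, censored as in Section 5. And/or repeat the primary analysis in all subjects with data cut at 8 May 2017. In simulation at true 1.15 with 7- and 8-year accrual, these return 1.149 and 1.149–1.150.
- Drop the OS HR in subjects still followed on 7 June. The tabulation by arm of subjects still on study, already planned in Section 9.2, serves that purpose.
- State one definition of affected and not affected per endpoint, so that Sections 4.2, 9.6.1 and 9.6.2 agree. The transfusion and dosing definitions in Section 4.2 need the same alignment with Sections 9.5.2 and 9.6.10.
- Reconcile the 22 June 2017 date in Appendix A with the 7 June 2017 end of data collection.

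The cost is SAP wording and one flag based on randomization date; no new data are needed. With the 12-month example and 7- or 8-year accrual, about 2185 or 2230 subjects remain (14% or 12–13% fewer), and the OS standard error is about 0.049–0.050 against 0.047–0.048. The 8 May cut gives up one month of follow-up.
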